8.3.9.1 Management Guidelines for Skin Toxicity for RO7296682 and/or atezolizumab

Treatment-emergent rash may be associated with RO7296682 and/or atezolizumab.

In study WP41188, skin-related AEs were observed in 42% of the patients treated up to a dose level of █ mg. The majority of cases of rash were mild in severity and self-limited, with or without pruritus (see [Investigator's Brochure](#)).

Participants should be advised to implement particular care of the skin and refer to the study staff in case of dermatologic issues especially after biopsy. After biopsy, study staff should protect the skin and ensure that prevention of superinfections is applied.

A dermatologist should evaluate persistent and/or severe rash or pruritus. A biopsy should be considered unless contraindicated. Management guidelines for dermatologic events are provided in [Table 11](#).

Table 11 Management Guidelines for Skin Toxicity

Event	Management
Dermatologic event, Grade 1	
 Continue RO7296682 and/or atezolizumab. Consider treatment with topical corticosteroids and/or other symptomatic therapy (e.g., antihistamines). Recommend taking anonymized standard clinical photography
Dermatologic event, Grade 2	
 Hold RO7296682 and/or atezolizumab until resolution to Grade 1 or baseline. Consider participant referral to a dermatologist. Initiate treatment with topical corticosteroids. Consider treatment with oral and/or higher-potency topical corticosteroids if event does not improve. Recommend taking anonymized standard clinical photography
Dermatologic event, Grade 3	
 Withhold RO7296682 and/or atezolizumab after event onset.^a Refer participant to a dermatologist. Initiate treatment with corticosteroids equivalent to 10 mg/day oral prednisone, increasing dose to 1 to 2 mg/kg/day if event does not improve within 48 to 72 hours. If event resolves to Grade 1 or better, resume RO7296682 and/or atezolizumab. If corticosteroids have been initiated, they must be tapered over ≥ 1 month to the equivalent of ≤ 10 mg/day oral prednisone before RO7296682 and/or atezolizumab can be resumed. If event does not resolve to Grade 1 or better while withholding RO7296682 and/or atezolizumab, permanently discontinue RO7296682 and/or atezolizumab and contact Medical Monitor.^b Recommend taking anonymized standard clinical photography
Dermatologic event, Grade 4	
 Permanently discontinue RO7296682 and/or atezolizumab and contact Medical Monitor.^b Recommend taking anonymized standard clinical photography

^a RO7296682 and/or atezolizumab may be withheld for a longer period (i.e., > 12 weeks after event onset) to allow for corticosteroids (if initiated) to be reduced to the equivalent of ≤ 10 mg/day oral prednisone. The acceptable length of the extended period must be agreed upon by the Investigator and the Medical Monitor.

^b Resumption of RO7296682 and/or atezolizumab may be considered in participants who are deriving benefit and have fully recovered from the immune-mediated event. Participants can be re-challenged with RO7296682 and/or atezolizumab only after approval has been documented by the Investigator (or an appropriate delegate) and the Medical Monitor.

8.3.9.2 Management Guidelines for Infusion-Related Reactions/Cytokine-Release Syndrome for RO7296682 and/or Atezolizumab

Administration of therapeutic antibodies may cause IRRs, which may include symptoms such as fever, chills, hypotension, shortness of breath, skin rash, headache, nausea, and vomiting. Such reactions typically occur during or shortly after the infusion, predominantly the first infusion. The incidence and severity typically decrease with subsequent infusions.

No premedication is indicated for the administration of Cycle 1 of RO7296682 and/or atezolizumab. However, patients who experience an infusion-related reaction (IRR) or cytokine release syndrome (CRS) with RO7296682 and/or atezolizumab may receive premedication with antihistamines, antipyretic medications, and/or analgesics (e.g., acetaminophen) for subsequent infusions. Metamizole (dipyrone) is prohibited in treating RO7296682 and/or atezolizumab-associated IRRs because of its potential for causing agranulocytosis.

IRRs are known to occur with the administration of mAbs and may be reported with RO7296682 and/or atezolizumab. These reactions, which are thought to be due to release of cytokines and/or other chemical mediators, occur within 24 hours of administration and are generally mild to moderate in severity.

CRS is defined as a supraphysiologic response following administration of any immune therapy that results in activation or engagement of endogenous or infused T cells and/or other immune effector cells. Symptoms can be progressive, always include fever at the onset, and may include hypotension, capillary leak (hypoxia), and end-organ dysfunction (Lee et al. 2019). CRS has been well documented with chimeric antigen receptor T-cell therapies and bispecific T-cell engager antibody therapies but has also been reported with immunotherapies that target PD-1 or PD-L1 (Rotz et al. 2017; Adashek and Feldman 2019), including atezolizumab.

There may be significant overlap in signs and symptoms of IRRs and CRS, and in recognition of the challenges in clinically distinguishing between the two, consolidated guidelines for the medical management of IRRs and CRS are provided in Table 12.

Severe COVID-19 appears to be associated with a CRS involving the inflammatory cytokines interleukin (IL)-6, IL-10, IL-2, and IFN- γ (Merad and Martin 2020). If a participant develops suspected CRS during the study, a differential diagnosis should include COVID-19, which should be confirmed or refuted through assessment of exposure history, appropriate laboratory testing, and clinical or radiologic evaluations per Investigator's judgment. If a diagnosis of COVID-19 is confirmed, the disease should be managed as per local or institutional guidelines.

Table 12 Management Guidelines for Infusion-Related Reactions and Cytokine-Release Syndrome

Event	Management
Grade 1^a Fever ^b with or without constitutional symptoms	
 Immediately interrupt infusion. Upon symptom resolution, wait for 30 minutes and then restart infusion at half the rate being given at the time of event onset. If the infusion is tolerated at the reduced rate for 30 minutes, the infusion rate may be increased to the original rate. If symptoms recur, discontinue infusion of this dose. Administer symptomatic treatment,^c including maintenance of IV fluids for hydration. In case of rapid decline or prolonged CRS (>2 days) or in participants with significant symptoms and/or comorbidities, consider managing as per Grade 2. For subsequent infusions, consider administration of oral pre-medication with antihistamines, antipyretic medications, and/or analgesics, and monitor closely for IRRs and/or CRS.
Grade 2^a Fever ^b with hypotension not requiring vasopressors and/or Hypoxia requiring low-flow oxygen ^d by nasal cannula or blow-by	
 Immediately interrupt infusion. Upon symptom resolution, wait for 30 minutes and then restart infusion at half the rate being given at the time of event onset. If symptoms recur, discontinue infusion of this dose. Administer symptomatic treatment.^c For hypotension, administer IV fluid bolus as needed. Monitor cardiopulmonary and other organ function closely (in the ICU, if appropriate). Administer IV fluids as clinically indicated, and manage constitutional symptoms and organ toxicities as per institutional practice. Rule out other inflammatory conditions that can mimic CRS (e.g., sepsis). If no improvement within 24 hours, initiate workup and assess for signs and symptoms of HLH or MAS as described in Appendix 12. Consider IV corticosteroids (e.g., methylprednisolone 2 mg/kg/day or dexamethasone 10 mg every 6 hours). Consider anti-cytokine therapy.^e Consider hospitalization until complete resolution of symptoms. If no improvement within 24 hours, manage as per Grade 3, that is, hospitalize participant (monitoring in the ICU is recommended), permanently discontinue RO7296682 and/or atezolizumab, and contact the Medical Monitor. If symptoms resolve to Grade 1 or better for three consecutive days, the next dose of RO7296682 and/or atezolizumab may be administered. For subsequent infusions, consider administration of oral pre-medication with antihistamines, antipyretic medications, and/or analgesics and monitor closely for IRRs and/or CRS. If symptoms do not resolve to Grade 1 or better for three consecutive days, contact the Medical Monitor.

Event	Management
Grade 3^a Fever ^b with hypotension requiring a vasopressor (with or without vasopressin) and/or Hypoxia requiring high-flow oxygen ^d by nasal cannula, face mask, non-rebreather mask, or Venturi mask	
 Permanently discontinue RO7296682 and/or atezolizumab and contact the Medical Monitor.^f Administer symptomatic treatment.^c For hypotension, administer IV fluid bolus and vasopressor as needed. Monitor cardiopulmonary and other organ function closely; monitoring in the ICU is recommended. Administer IV fluids as clinically indicated, and manage constitutional symptoms and organ toxicities as per institutional practice. Rule out other inflammatory conditions that can mimic CRS (e.g., sepsis). If no improvement within 24 hours, initiate workup and assess for signs and symptoms of HLH or MAS as described in Appendix 12. Administer IV corticosteroids (e.g., methylprednisolone 2 mg/kg/day or dexamethasone 10 mg every 6 hours). Consider anti-cytokine therapy.^e Hospitalize participant until complete resolution of symptoms. If no improvement within 24 hours, manage as per Grade 4, that is, admit participant to ICU and initiate hemodynamic monitoring, mechanical ventilation, and/or IV fluids and vasopressors as needed. For participants who are refractory to anti-cytokine therapy, experimental treatments may be considered at the discretion of the Investigator and in consultation with the Medical Monitor.
Grade 4^a Fever ^b with hypotension requiring multiple vasopressors (excluding vasopressin) and/or Hypoxia requiring oxygen by positive pressure (e.g., CPAP, BiPAP, intubation and mechanical ventilation)	
 Permanently discontinue RO7296682 and/or atezolizumab and contact the Medical Monitor.^f Administer symptomatic treatment.^c Admit participant to ICU and initiate hemodynamic monitoring, mechanical ventilation, and/or IV fluids and vasopressors as needed. Monitor other organ function closely. Manage constitutional symptoms and organ toxicities as per institutional practice. Rule out other inflammatory conditions that can mimic CRS (e.g., sepsis). If no improvement within 24 hours, initiate workup and assess for signs and symptoms of HLH or MAS as described in Appendix 12. Administer IV corticosteroids (e.g., methylprednisolone 2 mg/kg/day or dexamethasone 10 mg every 6 hours). Consider anti-cytokine therapy.^e For participants who are refractory to anti-cytokine therapy, experimental treatments^g may be considered at the discretion of the Investigator and in consultation with the Medical Monitor. Hospitalize participant until complete resolution of symptoms.

Table 12 Management Guidelines for Infusion-Related Reactions and Cytokine-Release Syndrome (Cont.)

ASTCT = American Society for Transplantation and Cellular Therapy; BiPAP = bi-level positive airway pressure; CAR = chimeric antigen receptor; CPAP = continuous positive airway pressure; CPI = checkpoint inhibitor; CRS = cytokine-release syndrome; CTCAE = Common Terminology Criteria for Adverse Events; eCRF = electronic Case Report Form; HLH = hemophagocytic lymphohistiocytosis; ICU = intensive care unit; IRR = infusion-related reaction; IV = intravenous; MAS = macrophage activation syndrome; NCCN = National Cancer Comprehensive Network; NCI = National Cancer Institute.

Note: The management guidelines have been adapted from the NCCN guidelines for the management of CAR T-cell–related toxicities (Version 2.2019).

- ^a Grading system for management guidelines is based on ASTCT consensus grading for CRS. NCI CTCAE v 5.0 should be used when reporting severity of IRRs, CRS, or organ toxicities associated with CRS on the Adverse Event eCRF. Organ toxicities associated with CRS should not influence overall CRS grading.
- ^b Fever is defined as temperature $\geq 38^{\circ}\text{C}$ not attributable to any other cause. In participants who develop CRS and then receive anti-pyretic, anti-cytokine, or corticosteroid therapy, fever is no longer required when subsequently determining event severity (grade). In this case, the grade is driven by the presence of hypotension and/or hypoxia.
- ^c Symptomatic treatment may include oral or IV antihistamines, *antipyretic medications*, analgesics, bronchodilators, and/or oxygen. For bronchospasm, urticaria, or dyspnea, additional treatment may be administered as per institutional practice.
- ^d Low flow is defined as oxygen delivered at ≤ 6 L/min, and high flow is defined as oxygen delivered at > 6 L/min.
- ^e There are case reports where anti-cytokine therapy has been used for treatment of CRS with immune CPIs (Rotz et al. 2017; Adashek and Feldman 2019), but data are limited, and the role of such treatment in the setting of antibody-associated CRS has not been established.
- ^f Resumption of RO7296682 and/or atezolizumab may be considered in participants who are deriving benefit and have fully recovered from the event. Participants can be re-challenged with RO7296682 and/or atezolizumab only after approval has been documented by the Investigator (or an appropriate delegate) and the Medical Monitor. For subsequent infusions, administer oral pre-medication with antihistamines, *antipyretic medications*, and/or analgesics, and monitor closely for IRRs and/or CRS. Pre-medication with corticosteroids and extending the infusion time may also be considered after consulting the Medical Monitor and considering the benefit–risk ratio.
- ^g Refer to Riegler et al. (2019) for information on experimental treatments for CRS.

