6.6 DOSE MODIFICATION

If, in the opinion of the Investigator, a toxicity is considered due solely to one of the study treatments, the dose of the other study treatment does not require modification.

However, in cases potentially related to both drugs, treatment with both RO7296682 and atezolizumab should be modified or permanently discontinued as appropriate based on the grade of toxicity. Examples of potentially overlapping toxicities that could be related to both drugs include immune-mediated toxicities, IRR/CRS, skin toxicity and immunogenicity.

For Part I (Dose-Escalation):

Dose-Limiting Toxicities (DLTs): Participants who experience toxicities fulfilling the definition of a DLT during the DLT assessment period should be discontinued from study treatment. Nevertheless, the Investigator, after discussion with the Sponsor, will have the option to reduce the dose of RO7296682 to the previous tolerated dose level, if participant is deemed to be deriving clinical benefit. No dose modification for atezolizumab is allowed.

For All Parts:

IMP-related AEs (i.e., attributed to RO7296682 in combination with atezolizumab): AEs attributable to IMPs must resolve to \leq Grade 1 or baseline for non-hematological toxicities and \leq Grade 2 for hematological toxicities before resuming treatment. Exceptions may be allowed after a careful potential clinical risk/benefit assessment by the Investigator and approval by the Medical Monitor.

Dose reduction of RO7296682 alone may be allowed with the approval of the Medical Monitor. No dose modification for atezolizumab is allowed.

AEs not attributed to IMPs: A delay of IMP administration for up to two cycles will be acceptable to allow for resolution of toxicity to NCI CTCAE Grade \leq 2 for hematological toxicities or Grade \leq 1 for non-hematological toxicities. If in the judgment of the Investigator, a participant is likely to derive clinical benefit from RO7296682 in combination with atezolizumab after a hold of more than 2 cycles, study drug may be re-started with the approval of the Medical Monitor.

Liver Function Tests: For participants with documented liver metastasis and elevated liver function test (LFT) results at baseline, further elevations of LFT results may not require dose interruptions if there are no progressive changes in the ALT and/or AST (less than a doubling) and if there are no progressive elevations in total bilirubin or international normalized ratio.

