Severe COVID-19 appears to be associated with a CRS involving the inflammatory cytokines IL-6, IL-10, IL-2, and IFN- γ ([Merad and Martin 2020](#)). If a participant develops suspected CRS during the study, a differential diagnosis should include COVID-19, which should be confirmed or refuted through assessment of exposure history, appropriate laboratory testing, and clinical or radiologic evaluations per Investigator judgment. If a diagnosis of COVID-19 is confirmed, the disease should be managed as per local or institutional guidelines.

For events in which management guidelines are not covered in this protocol, participants should be managed as deemed appropriate by the Investigator according to best medical judgment and local medical guidelines. Clinical judgment may be applied, and a risk/benefit consideration may suggest deviating from these guidelines. In this specific case, decisions on study treatments will be taken by the Investigator upon consultation with the Medical Monitor.

Guidelines for management of specific AEs are provided in [Table 11](#), [Table 12](#), and [Appendix 12](#).

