- ^b If corticosteroids have been initiated, they must be tapered over ≥ 1 month to the equivalent of ≤ 10 mg/day oral prednisone RO7296682 and/or atezolizumab can be resumed.
- ^c Resumption of RO7296682 and/or atezolizumab may be considered in participants who are deriving benefit and have fully recovered from the immune-mediated event. Participants can be re-challenged with RO7296682 and/or atezolizumab only after approval has been documented by the Investigator (or an appropriate delegate) and the Medical Monitor.

DERMATOLOGIC EVENTS

The majority of cases of rash *reported with the use of atezolizumab* were mild in severity and self-limited, with or without pruritus. A dermatologist should evaluate persistent and/or severe rash or pruritus. A biopsy should be considered unless contraindicated. Management guidelines for dermatologic events are provided in [Table 8](#).

Table 8 Management Guidelines for Dermatologic Events

Event	Management
Dermatologic event, Grade 1	
Continue RO7296682 and/or atezolizumab.Consider treatment with topical corticosteroids and/or other symptomatic therapy (e.g., antihistamines).
Dermatologic event, Grade 2	
Continue RO7296682 and/or atezolizumab.Consider patient referral to dermatologist.Initiate treatment with topical corticosteroids.Consider treatment with higher-potency topical corticosteroids if event does not improve.
Dermatologic event, Grade 3	
Withhold RO7296682 and/or atezolizumab after event onset.^aRefer participant to dermatologist.Initiate treatment with corticosteroids equivalent to 10 mg/day oral prednisone, increasing dose to 1–2 mg/kg/day if event does not improve within 48–72 hours.If event resolves to Grade 1 or better, resume RO7296682 and/or atezolizumab.^bIf event does not resolve to Grade 1 or better while withholding RO7296682 and/or atezolizumab, permanently discontinue RO7296682 and/or atezolizumab and contact the Medical Monitor.^c
Dermatologic event, Grade 4	
Permanently discontinue RO7296682 and/or atezolizumab and contact the Medical Monitor.^c

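### For a Grade 2 dermatologic event, Table 11 says hold dosing and Appendix 12 Table 8 says continue; no text says which applies

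*Combined protocol and SAP*

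**What the plan says.** Two tables in the combined protocol and SAP cover dermatologic events, and both label the row in question as Grade 2.

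- **Section 8.3.9.1, Table 11.** Dosing: "Hold RO7296682 and/or atezolizumab until resolution to Grade 1 or baseline". If there is no improvement: "Consider treatment with oral and/or higher-potency topical corticosteroids if event does not improve".
- **Appendix 12, Dermatologic Events, Table 8.** Dosing: "Continue RO7296682 and/or atezolizumab". If there is no improvement: "Consider treatment with higher-potency topical corticosteroids if event does not improve".

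Section 8.3.9 introduces its list of sources with "Guidelines for management of specific AEs are provided in" and then names Table 11, Table 12 and Appendix 12 together, in no order of precedence. Section 8.3.9.1 and the dermatologic part of Appendix 12 each name their own table as the place to find guidance on dermatologic events.

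Section 6.6 bears on the question in three ways. It says that if "a toxicity is considered due solely to one of the study treatments, the dose of the other study treatment does not require modification". It also says "Examples of potentially overlapping toxicities that could be related to both drugs include immune-mediated toxicities, IRR/CRS, skin toxicity and immunogenicity". And for IMP-related AEs it sets a condition for resuming treatment: resolution to "Grade 1 or baseline for non-hematological toxicities and" a separate threshold for hematological ones.

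**The concern.** A site with a participant who has a Grade 2 rash on a dosing day can look up either table, follow it exactly, and be compliant. One site would hold treatment and the other would dose. Section 8.3.9 calls for consultation with the Medical Monitor when a site departs from the guidelines, but a site following either table has not departed from them, so that safeguard is not triggered.

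Section 8.3.9 lists skin toxicity among the most common toxicities expected from RO7296682. It also states that this is the first human evaluation of the combination and that the combined risk is unknown. What is at stake is consistent protection of participants, and safety data collected under a single dosing rule.

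**Working it through.** No arithmetic beyond a count applies. The check sets the two tables side by side and then looks for text that would decide between them.

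**Step 1: dosing action by grade**

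| Grade | Table 11 (Section 8.3.9.1) | Table 8 (Appendix 12) | Agree? |
|---|---|---|---|
| 1 | Continue | Continue | Yes |
| 2 | Hold until Grade 1 or baseline | Continue | **No** |
| 3 | Withhold | Withhold | Yes |
| 4 | Permanently discontinue | Permanently discontinue | Yes |

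Agreement is 3 of 4 and conflict is 1 of 4. Both Grade 2 rows name both drugs, joined by and/or.

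**Step 2: steroid step at Grade 2.** Both rows start topical corticosteroids. If the event does not improve, Table 11 offers oral and/or higher-potency topical corticosteroids, and Table 8 offers only higher-potency topical ones.

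**Step 3: does scope separate the tables?**
- *By drug:* the lead-in to the dermatologic part of Appendix 12 speaks of rash seen with atezolizumab. But the Appendix 12 title covers RO7296682 and the combination, and Table 8 instructs on RO7296682 too. Section 8.3.9.1 covers rash associated with either drug.
- *By mechanism:* Appendix 12 is for immune-mediated events and Section 8.3.9.1 for skin toxicity. But footnote b of Table 11 concerns recovery from an immune-mediated event, and Section 8.3.9.3 lists skin among the organs most often affected by such events. The scopes overlap.

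**Step 4: does any text set precedence?**
- Section 8.3.9 lists the sources unranked. Section 6.5.1 likewise sends sites to both Section 8.3.9.1 and Appendix 12 for corticosteroid use.
- Section 8.3.9.1 points only to Table 11, which favours holding.
- Section 6.6 favours holding for IMP-related events, but it sets the condition for resuming, allows exceptions with Medical Monitor approval, and names neither table.
- The drug-by-drug rule in Section 6.6 applies when one drug is solely responsible. The same section names skin toxicity as potentially due to both, and in that case the tables give opposite instructions.

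Three texts therefore lean towards holding: the two Section 6.6 statements (skin toxicity as overlapping, and the condition for resuming) and the Section 8.3.9.1 pointer. None settles the matter.

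**Step 5: how often would it matter?** The only figure is in Section 8.3.9.1: 42% of patients in the single-agent study WP41188 had skin-related AEs. It is all-grade, gives no Grade 2 share, and comes with the statement that most rash was mild and self-limited. No frequency for this event in the combination can be derived. Dosing is every 21 days, so the tables lead to different dosing only if the event is still Grade 2 on a dosing day.

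**Step 6: a conditional effect in Part I.** Under Section 4.1.2 and Table 13, a participant without a DLT is DLT-evaluable only after two administrations, and the second may be delayed by at most 2 days if the SDEC agrees. If a Grade 2 rash persisted beyond that allowance, Table 11 could make the participant non-evaluable and subject to replacement, while Table 8 would keep the participant evaluable. This depends on the timing of the rash, and its frequency cannot be estimated.

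**The case against.** The strongest reply is that the tables have different scopes that were simply not labelled. The protocol lists skin toxicity separately from immune-mediated toxicities in Sections 6.6 and 8.3.9, gives it its own section, and reaches Appendix 12 through the immune-mediated section, 8.3.9.3. The reference to atezolizumab in the Appendix 12 lead-in is in the italics that mark new information in Version 4, which suggests a deliberate atezolizumab focus. Because both rows say and/or, holding RO7296682 while continuing atezolizumab would satisfy both literally. Section 6.1 names Section 6.6 as the place for dosage modification, and Section 6.6 agrees with Table 11.

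The reply also limits the consequences. Many rashes may settle within the 21-day cycle. Dosing agrees at Grades 3 and 4. After Cycle 1, RO7296682 dose modifications should be discussed with the Sponsor (Section 6.6), and restart after an interruption follows discussion with the Medical Monitor (Section 7.1.1). Replacement rules already cover lost DLT evaluability. Finally, changing Table 8 to a hold would decide a clinical question about atezolizumab that these documents do not decide.

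Much of this stands as a limit on how often the conflict matters, and a missing scope label may well be its origin. It does not remove the conflict. Neither row says which drug it governs, and Table 8 still tells the site to continue RO7296682. Section 6.6 governs resuming and does not order a hold. The consultation steps apply to modifying or restarting treatment, so they do not clearly catch a site that simply continues. The remark about the clinical question is fair, and the fix therefore includes a route that leaves drug-specific handling open.

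**Conclusion.** The concern holds. For an identically labelled Grade 2 dermatologic event, two current tables give opposite dosing instructions and different steroid steps, and no text ranks them or separates their scopes. The dosing conflict is confined to 1 of 4 grades. The number of participants affected is unknown, and no endpoint, sample size or decision rule is claimed to change. The conclusion rests on the wording of the two tables and on the absence of a precedence or scope rule in Sections 6.5.1, 6.6, 8.3.9, 8.3.9.1, 8.3.9.3 and Appendix 12. The Investigator's Brochures were not available and might show which action was intended. The point should be fixed: it is a contradictory dosing rule for an expected toxicity in a first-in-human combination.

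**What to change.** Either of two changes resolves it.

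1. **One rule.** Change the Grade 2 row of Appendix 12 Table 8 to hold until Grade 1 or baseline, with the same corticosteroid options as Table 11, or delete Table 8 and cross-refer to Table 11. This agrees with the resumption condition in Section 6.6. Section 8.3.9.2 already uses a single consolidated table for infusion-related reactions and cytokine-release syndrome.
2. **Drug-specific rule, if intended.** State in both Grade 2 rows which drug is held and which is continued, align or explain the steroid options, and say in Section 8.3.9 which table prevails when causality is shared or unclear.

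The sponsor's clinical and safety staff should choose between them against the Investigator's Brochures. The cost is clarification wording in the protocol, with no effect on data collection or sample size.
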